This is a prospective randomized trial to test the efficacy of preemptive Rituxan in melanoma patients in reducing Immune-related adverse events (IRAEs) following combination checkpoint blockade (CCB). All eligible patients will undergo baseline evaluation to assess the status of disease as well as a baseline tumor biopsy. Combination checkpoint blockade will be administered as per current FDA approved standard of care, consisting of nivolumab at a dose of 1 mg/kg and ipilimumab at a dose of 3 mg/kg every 3 weeks for 4 doses, followed by nivolumab maintenance at a dose of 480 mg every 4 weeks x 1 year. Patients will be randomly assigned to no additional therapy (ARM A control) or 4 weekly doses of Rituxan for B cell depletion (ARM B). Rituxan will be administered as 375 mg/m2 IV for the first dose followed by weekly subcutaneous dosing at 1400 mg dose of Rituxan Hycela for weeks 2-4, as per recommended dosing for the FDA approval in the setting of lymphoma. All patients will be clinically monitored for the development of IRAEs utilizing NCI Common Toxicity Criteria v5.0. Any patient who received at least one dose of study drug will be included in safety analysis, and safety assessment will continue through treatment phase and up to 100 days after the last dose of study drug. Tumor response will be assessed according to the Response Evaluation Criteria in Solid Tumors (RECIST v1.1) and irRECIST at 12 weeks and every 12 weeks thereafter. All patients will also undergo pre treatment and post treatment biopsies if possible.

TABLE OF CONTENTS

SCH	EMA	3								
1.	OBJECTIVES	6								

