7.2 Adverse Event Characteristics

SAFETY REPORTING OF ADVERSE EVENTS

ASSESSMENT OF SAFETY

Specification of Safety Variables

Safety assessments will consist of monitoring and reporting adverse events (AEs) and serious adverse events (SAEs) per protocol. This includes all events of death, and any study specific issue of concern.

Adverse Events

An AE is any unfavorable and unintended sign (including an abnormal laboratory finding), symptom, or disease temporally associated with the use of an investigational medicinal product (IMP) or other protocol-imposed intervention, regardless of attribution.

This includes the following:

- AEs not previously observed in the subject that emerges during the protocol-specified AE reporting period, including signs or symptoms associated with melanoma those were not present prior to the AE reporting period.
- Complications that occur as a result of protocol-mandated interventions (e.g., invasive procedures such as cardiac catheterizations)
- If applicable, AEs that occur prior to assignment of study treatment associated with medication washout, no treatment run-in, or other protocol-mandated intervention.
- Preexisting medical conditions (other than the condition being studied) judged by the
- Investigator to have worsened in severity or frequency or changed in character during the protocol-specified AE reporting period.

Serious Adverse Events

An AE should be classified as an SAE if the following criteria are met:

- It results in death (i.e., the AE actually causes or leads to death).
- It is life threatening (i.e., the AE, in the view of the investigator, places the subject at immediate risk of death. It does not include an AE that, had it occurred in a more severe form, might have caused death.).
- It requires or prolongs inpatient hospitalization.
- It results in persistent or significant disability/incapacity (i.e., the AE results in substantial disruption of the subject's ability to conduct normal life functions).
- It results in a congenital anomaly/birth defect in a neonate/infant born to a mother exposed to the IMP.
- It is considered a significant medical event by the investigator based on medical judgment (e.g., may jeopardize the subject or may require medical/surgical intervention to prevent one of the outcomes listed above).

METHODS AND TIMING FOR ASSESSING AND RECORDING SAFETY VARIABLES

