The investigator is responsible for ensuring that all AEs and SAEs that are observed or reported during the study are collected and reported to the FDA, appropriate IRB(s), and Genentech, Inc.in accordance with CFR 312.32 (IND Safety Reports).

Adverse Event Reporting Period

The study period during which AEs and SAEs must be reported begins after informed consent is obtained and initiation of study treatment and ends 30 days following the last administration of study treatment or study discontinuation/termination, whichever is earlier. After this period, investigators should only report SAEs that are attributed to prior study treatment.

Assessment of Adverse Events

All AEs and SAEs whether volunteered by the subject, discovered by study personnel during questioning, or detected through physical examination, laboratory test, or other means will be reported appropriately. Each reported AE or SAE will be described by its duration (i.e., start and end dates), regulatory seriousness criteria if applicable, suspected relationship to the Rituxan IV/Rituxan Hycela (see following guidance), and actions taken.

To ensure consistency of AE and SAE causality assessments, investigators should apply the following general guideline:

Yes

There is a plausible temporal relationship between the onset of the AE and administration of Rituxan IV/Rituxan Hycela , and the AE cannot be readily explained by the subject's clinical state, intercurrent illness, or concomitant therapies; and/or the AE follows a known pattern of response to Rituxan IV/Rituxan Hycela; and/or the AE abates or resolves upon discontinuation of Rituxan IV/Rituxan Hycela, or dose reduction and, if applicable, reappears upon rechallenge.

No

Evidence exists that the AE has an etiology other than Rituxan IV/Rituxan Hycela (e.g., preexisting medical condition, underlying disease, intercurrent illness, or concomitant medication); and/or the AE has no plausible temporal relationship to Rituxan IV/Rituxan Hycela administration (e.g., cancer diagnosed 2 days after first dose of study drug).

Expected adverse events are those adverse events that are listed or characterized in the Package Insert (P.I) or current Investigator Brochure (I.B).

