10.1 Laboratory Correlative Studies

- 10.1.1 Title Peripheral Blood for immune analysis to be drawn any time prior to the cycle of treatment as long as it's the same day as treatment
- 10.1.1.1 Collection of Specimen(s): collect 40-60 ml in green top heparin anticoagulant.
- 10.1.1.2 Handling of Specimens(s): keep at room temperature.
- 10.1.1.3 Shipping of Specimen(s): call [name] lab for pickup.
- 10.1.1.4 Site(s) Performing Correlative Study; [name] lab

10.1.2 *Title – Tissue for immune analysis*

- 10.1.2.1 Collection of Specimen(s): Fresh tissue from operating room
- 10.1.2.2 Handling of Specimens(s): keep at room temperature.
- 10.1.2.3 Shipping of Specimen(s): call [name] lab for pickup.
- 10.1.2.4 Site(s) Performing Correlative Study: [name] lab.

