11. STUDY CALENDAR

Schedules shown in the Study Calendar below are provided as an example and should be modified as appropriate.

Baseline evaluations are to be conducted within 3 weeks prior to start of protocol therapy. Scans and x-rays must be done \leq 4 weeks prior to the start of therapy. In the event that the patient's condition is deteriorating, laboratory evaluations should be repeated within 48 hours prior to initiation of the next cycle of therapy.

All protocol visits have a plus or minus 3 business day window.

Rituxan should be given after ipi/nivo infusion for subjects on Arm B. The timing of Rituxan is 1-2 days (preferably 1 day) following ipi-nivo infusion.

		1	ı	ı						1	1					
	Pre- Study	Wk 1	Wk 2	Wk 3	Wk 4	Wk 5	Wk	Wk	Wk 8	Wk 9	Wk 10	WK 12	Wk 13	WK 17	WK 21	Off Study
IPI 3mg/kg + Nivo 1mg/kg		X			X			X			X					
Nivo 480mg IV ^a													X	X	X	
Rituxan IV (loading dose)			X													
Rituxan SQ				X	X	X										
Informed consent	X															
Demographics	X															
Medical history	X															
Con Medications	X	X	X	X	X			X			X		X	X	X	X
Physical exam	X	X			X			X			X		X	X	X	X
Vital signs	X	X	X	X	X			X			X		X	X	X	X
Height	X															
Weight	X	X	X	X	X			X			X		X	X	X	X
Performance status	X	X			X			X			X		X			X
CBC w/diff, plts	X	X	X	X	X			X			X		X	X	X	X
Serum chemistry with LDH	X	X	X	X	X			X			X		X	X	X	X
EKG (12-lead)	X															
Adverse Event	X	X	X	X	X			X			X		X	X	X	X
Radiologic Evaluation ^b	X											X				
B-HCG	X															
Hepatitis B (HepB surface antigen and HepB core antibody), Hep C and HIV serology	X															
TSH, Free T, ACTH, cortisol	X				X			X			X		X	X	X	X
Blood correlative	X		X		X						X		X			X
Fresh Tissue Biopsy ^c	X				X											

^a given every 4 weeks starting at Week 13 for up to 13 doses.

^b CT scans n/c/a/p with contrast every 12 weeks for the first two years, then every 6 months for five years. MRI brain with contrast should be done at baseline, then every 6 months for patients with no history of CNS mets as per standard of care; every 3 months for those with a history of CNS metastases for two years, then every 6 months. CT head can be used for patients with a contraindication to MRI.

^C Tissue biopsy before week 4 is optional but encouraged whenever possible.

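### Mandatory AE/SAE reporting opens only once study treatment has started, which conflicts with the protocol's own AE definition, its Pre-Study adverse-event check and its unrestricted reporting rules, and leaves complications of the baseline research biopsy in doubt

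*Combined protocol and SAP*

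**What the plan says.** **Start of the reporting period.** Section 7.2 (Adverse Event Reporting Period) states: "The study period during which AEs and SAEs must be reported begins after informed consent is obtained and initiation of study treatment".

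**What counts as an AE.** Earlier in Section 7.2, the list of AEs includes "Complications that occur as a result of protocol-mandated interventions (e.g., invasive procedures such as cardiac catheterizations"), and then "If applicable, AEs that occur prior to assignment of study treatment associated with medication washout, no treatment run-in, or other protocol-mandated intervention".

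**The baseline biopsy.** The trial summary under the Schema says "All eligible patients will undergo baseline evaluation to assess the status of disease as well as a baseline tumor biopsy". The same paragraph ends with a softer statement: "All patients will also undergo pre treatment and post treatment biopsies if possible". The Section 11 calendar marks the row "Fresh Tissue Biopsy" at Pre-Study and at week 4, with a footnote: "Tissue biopsy before week 4 is optional but encouraged whenever possible". Section 10.1 lists "Tissue for immune analysis" among the correlative studies.

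**Other safety rules.** The calendar's adverse-event row is marked at Pre-Study. Section 7.2 gives the investigator a general duty covering AEs and SAEs seen in the course of the study. Section 7.3.2 requires immediate reporting of any SAE whatever its relationship to the agent, and of deaths on study whatever their cause. Section 7.4 routes every AE through ONCORE. None of these gives a start date. The Schema summary limits the safety analysis to patients with at least one dose of study drug, and Section 12.1.1 starts toxicity evaluability at the first ipilimumab/nivolumab treatment.

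**The concern.** The AE definition and the reporting period do not fit together. An event before treatment assignment necessarily comes before treatment starts, so the definition names a class of AE that the reporting period leaves out. In this trial the class is not empty, because a tumour biopsy is planned before treatment and its tissue serves the correlative work.

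At stake is oversight of harm from a research procedure. Two sites, both acting in good faith, could handle the same serious biopsy complication differently: one would report it under Section 7.3.2, and the other would treat it as outside the Section 7.2 period. If the complication prevents treatment from starting, the patient is also absent from the safety analysis, so the final tables would not bring the event to light.

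**Working it through.** The plan gives no figure to reproduce. The check sets the rules side by side for one case: a serious complication of the baseline biopsy, after consent and before the first dose.

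1. **Is it an AE?** Under Section 7.2, yes if the biopsy is a protocol-mandated intervention. The lead definition there is wider and also takes in interventions that the protocol imposes, so a biopsy taken for the correlative work reasonably falls within it even if it is optional.
2. **Is it inside the mandatory period?** No. The period needs consent and the start of study treatment, and the second has not occurred.
3. **Would a death be reported?** The paragraph on deaths in Section 7.2 covers those within the reporting period, which would leave this one out. Section 7.3.2 requires a report of any death on study. The two differ.
4. **Would the event be asked about?** Probably. The calendar has an adverse-event check at Pre-Study, and Section 7.2 asks for AEs to be elicited consistently at every evaluation.
5. **Would it be entered?** Section 7.4 says so, without a start date. The Section 7.2 period implies that entry is not obligatory.
6. **Would it be analysed?** Not if the patient never starts treatment: the Schema summary requires a dose, and Section 12.1.1 counts from the first ipilimumab/nivolumab treatment.

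**Length of the interval.** Section 11 allows baseline evaluations up to 3 weeks before protocol therapy. Counted back from the first ipilimumab/nivolumab dose, that is 3 × 7 = 21 days.

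**Which treatment opens the period?** Section 5.2 describes the protocol-specific therapy as rituximab alone. If that is what study treatment means in Section 7.2, and the baseline window still runs back from the first ipilimumab/nivolumab dose, the interval in Arm B grows. The documents disagree on the rituximab start, so two results follow:

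- Rituximab 1–2 days after ipilimumab/nivolumab (Schema; Section 11 text): 21 + 1 = 22 to 21 + 2 = 23 days.
- Rituximab 1 week after (Section 5.1): 21 + 7 = 28 days.

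These ignore visit windows. On this reading Arm A, which receives no rituximab, has no defined start at all. The two statements of rituximab timing need reconciling in their own right; nothing here depends on which one stands.

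**The case against.** The strongest reply is that the period sentence is one loose line among several broader duties. The Pre-Study adverse-event mark, the instruction on ONCORE, the rule on any SAE and the investigator's general duty all point towards capture. Section 4.1 registers patients at consent, so someone biopsied but never treated is already known to the study.

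Much of this stands. A reader might infer that such a patient would leave no safety record, or that the event is plainly exempt from reporting. The documents do not support either inference: they give overlapping and conflicting instructions, not a clear exemption. What the reply does not remove is the conflict. Section 7.2 is the one place that says when reporting becomes obligatory, and the broader duties have no start date that would override it.

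A second reply is that the biopsy may not be mandatory. The Schema qualifier and the calendar footnote do blur this, and it is unclear whether the footnote covers the Pre-Study biopsy or only the week 4 one. Section 10.1.2 says only that tissue comes fresh from the operating room, so some samples may not need a separate research procedure. This affects how many biopsies are at issue. It does not change how a complication of one done for the protocol should be handled.

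A reader might also be tempted to apply an assumed complication rate to all 44 patients and project a number of missed events. That is not supported. The 44 are the enrolment target, not a count of biopsies; patients biopsied but never randomised lie outside it; no complication rate is given; and a complication that first appears after dosing would fall inside the period.

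**Conclusion.** The point holds as an inconsistency in when safety reporting starts. The Section 7.2 period conflicts with the AE definition in the same section, with the Pre-Study adverse-event mark in Section 11, and with the unrestricted instructions in Sections 7.3.2 and 7.4. A serious biopsy complication before the first dose could go unreported by a site that follows the period as written, and the safety analysis would leave out a patient who never starts treatment.

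The size is an interval of up to 21 days per patient, assuming that study treatment means ipilimumab/nivolumab and that the biopsy falls within the baseline window. The number of events cannot be estimated from the documents.

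The primary endpoint, grade 3 or greater immune-related events at 6 months, is unaffected, because a biopsy complication before checkpoint therapy is not an immune-related event of that therapy. Randomisation and the efficacy analyses are also unaffected. The correction should be made for safety oversight and does not bear on the validity of the main comparison.

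**What to change.** Replace the start of the reporting period in Section 7.2 with:

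> *From signed informed consent, all SAEs (including deaths) and all AEs associated with protocol-specified procedures, including optional research biopsies, are reported. From the first dose of ipilimumab/nivolumab in both arms, all AEs are reported.*

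Then refer to this definition in Sections 7.3.2 and 7.4 and in the calendar's adverse-event row, so that all of them use the same start. Covering all SAEs from consent is deliberate: a narrower rule limited to procedure-related events would exclude unrelated SAEs and deaths before the first dose, against Section 7.3.2. Naming optional biopsies removes any dependence on whether the biopsy is mandatory, and naming ipilimumab/nivolumab gives both arms the same start for reporting.

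Tabulate events before the first dose separately from the treatment-emergent safety analysis, and include patients who never start treatment in that table.

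The cost is a two-sentence amendment with cross-references, one additional table, and a small amount of extra reporting between consent and first dose. Sample size, randomisation and the primary analysis do not change.

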1. OBJECTIVES

1.1 Primary Objectives

• To compare rates for Grade 3-4 IRAEs in the first 6 months in patients treated with combination checkpoint blockade (CCB) therapy (anti-CTLA4 and anti-PD1) as a part of standard of care for advanced melanoma who are treated with a single course of 4 weekly doses of Rituxan therapy versus those who are not treated with Rituxan.

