For studies involving collection of survival data the investigator after the end of the adverse event reporting period (defined as 30 days after the last dose of study drug) should report all deaths, (regardless of cause), and any serious adverse event including development of cancer or a congenital anomaly in a subsequently conceived offspring of a female subject including pregnancy occurring in the partner of a male study subject who participated in the study that is believed to be related to prior exposure to study drug.

Case Transmission Verification will be performed by both parties during this period to ensure successful transmission of Single case reports.

• CTCAE term (AE description) and grade: The descriptions and grading scales found in the revised NCI Common Terminology Criteria for Adverse Events (CTCAE) version 5.0

will be utilized for AE reporting. All appropriate treatment areas should have access to a copy of the CTCAE version 5.0.

Adverse Event Severity Grading Scale for Events Not Specifically Listed in NCI CTCAE

CICIL	
Grade	Severity
1	Mild; asymptomatic or mild symptoms; clinical or diagnostic
	observations only; or intervention not indicated
2	Moderate; minimal, local, or non-invasive intervention
	indicated; or limiting age-appropriate instrumental activities of
	daily living ^a
3	Severe or medically significant, but not immediately
	life-threatening; hospitalization or prolongation of
	hospitalization indicated; disabling; or limiting self-care
	activities of daily living b,c
4	Life-threatening consequences or urgent intervention indicated d
5	Death related to adverse event d

NCI CTCAE = National Cancer Institute Common Terminology Criteria for Adverse Events.

Note: Based on the most recent version of NCI CTCAE (v5.0), which can be found at:

http://ctep.cancer.gov/protocolDevelopment/electronic_applications/ctc.htm

- a. Instrumental activities of daily living refer to preparing meals, shopping for groceries or clothes, using the telephone, managing money, etc.
- b. Examples of self-care activities of daily living include bathing, dressing and undressing, feeding oneself, using the toilet, and taking medications, as performed by patients who are not bedridden.
- c. If an event is assessed as a "significant medical event," it must be reported as a serious adverse event
- d. Grade 4 and 5 events must be reported as serious adverse events

For expedited reporting purposes only:

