- "24-Hour; 5 Calendar Days" The AE must initially be reported to the IRB/FDA and Genentech within 24 hours of learning of the AE, followed by a complete expedited report within 5 calendar days of the initial 24-hour report.
- "10 Calendar Days" A complete expedited report on the AE must be submitted within 10 calendar days of learning of the AE.

¹Serious adverse events that occur more than 30 days after the last administration of investigational agent/intervention and have an attribution of possible, probable, or definite require reporting as follows:

Expedited 24-hour notification followed by complete report within 5 calendar days for:

• All Grade 3, 4, and Grade 5 AEs

Expedited 10 calendar day reports for:

• Grade 2 AEs resulting in hospitalization or prolongation of hospitalization

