14. STATISTICAL CONSIDERATIONS

14.1 Study Design/Endpoints

Endpoints:

Primary:

• Primary endpoint is the rate of CTC (v5.0) grade 3 or greater immune-related adverse events at 6 months of follow up.

Secondary:

- Rate of CTC (v5.0) toxicity related to Rituxan.
- Objective tumor response as assessed by RECIST v1.1 and irRECIST at 12 weeks and every 12 weeks thereafter.
- Rates of overall and progression-free survival at 1 year following initiation of therapy.

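### None of the stated adverse event periods is tied to the 6-month primary endpoint, so later grade 3 IRAEs, mainly non-serious ones, can go unrecorded in patients who stop treatment early

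*Combined protocol and SAP*

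**What the plan says.** **Endpoint.** Section 1.1 sets the objective: "To compare rates for Grade 3-4 IRAEs in the first 6 months". Section 14.1 repeats the time frame: "Primary endpoint is the rate of CTC (v5.0) grade 3 or greater immune-related adverse events at 6 months of follow up". Section 14.2 sizes the trial on the same 6-month rate.

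**Periods for adverse events and follow-up.**
- Section 7.2 gives a reporting period that "ends 30 days following the last administration of study treatment or study discontinuation/termination, whichever is earlier". It continues: "After this period, investigators should only report SAEs that are attributed to prior study treatment". The paragraph on post-study events restates "the end of the adverse event reporting period (defined as 30 days after the last dose of study drug").
- The Schema has safety assessment running through treatment and for up to 100 days beyond the final study drug dose.
- Section 5.3 follows patients for four weeks once they are off study. Those removed for unacceptable toxicity are followed until it resolves or stabilises. Section 5.4 ties removal to the list in Section 5.2, which includes progression.

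**Late reporting.** Under Section 7.3.2, serious events that "occur more than 30 days after the last administration of investigational agent/intervention and have an attribution of possible, probable, or definite require reporting". Section 7.2 adds: "Grade 4 and 5 events must be reported as serious adverse events". It does not make grade 3 events serious automatically.

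**Attribution.** The causality guidance in Section 7.2 concerns "suspected relationship to the Rituxan IV/Rituxan Hycela". A later sentence asks for causality to be judged separately for each protocol therapy.

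**Denominator.** The Schema puts everyone who had at least one study drug dose in the safety analysis. Section 12.1.1 makes all patients evaluable for toxicity from their first ipilimumab/nivolumab treatment. Section 14 does not say how a patient without 6 months of observation is coded.

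**The concern.** The endpoint counts events to month 6, but the collection rules run from the last dose or from removal. A site that follows Section 7.2 literally could stop recording non-serious adverse events well before month 6 in a patient who stopped early. An IRAE in that gap would count toward the endpoint and yet need not appear in the data.

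Two things are at stake. Loss shared equally by the arms lowers both observed rates and costs power. Loss that differs by arm biases the comparison. Separately, someone must decide whether a patient last checked at month 3 without an event is a non-event or unknown. In an open-label trial of 44 patients, that should be settled before the data are seen.

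**Working it through.** **1. The plan's own power.** Inputs from Section 14.2: 22 per arm, 60% versus 20%, Fisher's exact test, one-sided 0.05. Summing the two binomial distributions over all tables with one-sided p ≤ 0.05 gives 79.1%, which agrees with the stated figure of about 80%. Expected events are 22 × 0.60 = 13.2 in Arm A and 22 × 0.20 = 4.4 in Arm B.

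**2. Days covered.** Day 1 is the first ipilimumab/nivolumab dose, week w starts on day 7(w − 1) + 1, and 26 weeks is day 182. Dosing weeks come from the Section 11 calendar; week 25 follows from its four-weekly nivolumab. The table assumes that study treatment includes ipilimumab/nivolumab.

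| Last dose | Day | +30 days | +100 days |
|---|---|---|---|
| Induction dose 4 (week 10) | 64 | 94 | 164 |
| Week 13 | 85 | 115 | 185 |
| Week 21 | 141 | 171 | 241 |
| Week 25 | 169 | 199 | 269 |

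After induction dose 4, coverage is 94/182 = 52% or 164/182 = 90% of the endpoint period. For a last dose at week 21 it is 171/182 = 94% under the 30-day rule. That rule reaches day 182 only if the last dose is on or after day 182 − 30 = 152. The 100-day rule needs a last dose on or after day 182 − 100 = 82. If progression at the week-12 scan (about day 84) led to removal, the four-week rule would end follow-up near day 84 + 28 = 112.

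**3. Events exposed.** After the 30-day window, attributed serious events remain reportable, and grade 4 and 5 events are always serious. A patient who stopped because of a grade 3 or higher IRAE already counts. What remains is mainly non-serious grade 3 IRAEs, plus any that are not attributed, in patients who stopped before an event.

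**4. Effect on power.** The documents give no missed share, so the loss m is an assumption. With equal loss, the observed rates become 0.60(1 − m) and 0.20(1 − m).

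| m | Events lost, A / B | Power |
|---|---|---|
| 0 | 0 / 0 | 79.1% |
| 1% | 0.13 / 0.04 | 78.4% |
| 3% | 0.40 / 0.13 | 76.8% |
| 5% | 0.66 / 0.22 | 75.3% |
| 10% | 1.32 / 0.44 | 71.4% |

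**5. Effect on type I error.** Here the true rate is 60% in both arms, and the chance of wrongly declaring a lower rate in Arm B is:

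| Loss in A / B | Type I error |
|---|---|
| 0 / 0 | 2.3% |
| 10% / 10% | 2.4% |
| 0 / 5% | 3.7% |
| 5% / 10% | 3.8% |
| 0 / 10% | 5.7% |
| 10% / 20% | 5.8% |

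Fisher's test is conservative at this size, so equal loss and modest differences stay below 5%.

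**The case against.** The best defence is that reporting is not the same as ascertainment. The 30-day limit sits among rules for notifying the FDA, the IRB and the manufacturer, while the endpoint carries its own 6-month time frame. The Schema says all patients are monitored for IRAEs. Section 7.2 asks for adverse events to be elicited consistently at every evaluation, and 12-weekly scans put one near week 24. Section 6 keeps patients who stop rituximab for related toxicity under follow-up in their arm. One-year survival also implies later contact. All of this makes it likely that many late events would be noticed. None of it is a rule to collect adverse events to month 6 in patients who are off treatment or off study.

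Other parts of the defence stand:
- If ipilimumab/nivolumab is study treatment, an event judged immune-related would usually be attributed, so the unattributed group is small. The late-event list in Section 7.3.2 names all grade 3 to 5 events, but under a condition that they are serious.
- The criteria in Section 5.2 are written around the four rituximab doses or observation, and the first scheduled scan comes later. A reader might infer that every progressing patient leaves the study with four weeks of follow-up. The text does not settle that.
- A reader might infer that incomplete patients would be dropped, inflating both rates. The Schema and Section 12.1.1 point to keeping them in the denominator.
- A reader might take study treatment to mean rituximab alone, leaving Arm A with no anchor. Section 5.2 lends this some support, but the calendar's adverse event checks and the toxicity definition in Section 12.1.1 make it the less likely reading.

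**Conclusion.** The point holds within limits, and the plan should be corrected. The stated periods differ, none is tied to month 6, and study treatment is not defined. Under the 30-day rule, coverage falls short for anyone whose last dose is at week 21 or earlier. Under the 100-day rule, it falls short mainly for those who stop during induction, and by 18 days (182 − 164) after induction dose 4.

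The day counts rest on ipilimumab/nivolumab being study treatment. The effect on power, from 79% to between 78% and 71% for 1% to 10% equal loss, rests on assumed shares and is a range, not an estimate. A reader might infer that the false-positive rate is inflated. That needs a marked difference in loss between arms, and the documents give no evidence of one. Nor would all late severe events disappear, because attributed serious events remain reportable. The open analysis question is narrow: how to code event-free patients with incomplete 6-month follow-up, including those who die without a prior grade 3 or higher IRAE.

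**What to change.** - Reconcile the Schema and Sections 5.3, 5.4 and 7.2 into one adverse event collection period for the primary endpoint. It should apply to both arms, run from the first ipilimumab/nivolumab dose to week 26, and cover all grade 3 or higher events regardless of attribution, progression or stopping treatment, unless consent is withdrawn.
- Define study treatment, and separate coming off treatment from coming off study for adverse event follow-up. State whether progression after the rituximab doses triggers removal.
- Add a week-26 adverse event check, by chart review or call, to the Section 11 calendar.
- In Section 14.2, keep all treated patients in the denominator, state how incomplete event-free patients and deaths are coded, and add a sensitivity analysis under the opposite coding.

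The cost is protocol wording and one extra check for patients off treatment. No patients or procedures are added, and the sample size is unchanged.
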